TOTAL EXPECTED NUMBER OF PATIENTS	Phase I component- 9-18 patients Phase II component-38 patients
PRE-, DURING AND POST-THERAPY TISSUE AND SERUM COLLECTION (Phase II component only)	Serum samples will be drawn for measurement of angiogenic markers, alfa-fetoprotein and inflammatory cytokines pre, during and post therapy. When feasible core biopsies will be obtained for tissue banking for research purposes and for routine H&E staining, pre and during therapy.
STUDY DRUG FORMULATIONS	Bavituximab: supplied as a sterile, preservative-free solution with 10 mM acetate at pH 5.0 and diluted with 0.9% (w/v) saline to a final volume of 100 ml. Sorafenib: information per package insert.

ROUTE OF ADMINISTRATION	Bavituximab: Intravenous (IV) Sorafenib: Oral
DOSE REGIMEN	Bavituximab: 0.3 mg/kg, 1.0 mg/kg or 3.0 mg/kg IV over 90 minutes weekly. Sorafenib: Initial dose 200 mg PO twice daily to be escalated to the target dose of 400 mg PO twice daily Phase I: Bavituximab and sorafenib are to be given for 1 cycle or 4 weeks. Phase II: Bavituximab and sorafenib are to be continued until disease progression or toxicity.
EVALUATION CRITERIA	Primary: Phase I: safety as measured by adverse events Phase II: efficacy as measured by time to progression using RECIST Version 1.1. Secondary: Phase II: 
 1. Safety and tolerability as assessed by NCI CTC v4.0 of this regimen in the phase II setting. 2. Overall survival, response rate and progression-free survival. 3. Correlation of serum and tissue markers of angiogenesis and immune response with treatment response.
DURATION OF STUDY PERIOD	Phase I: Patients will continue study treatment until 1 cycle of therapy. Phase II: Patients will continue study treatment until disease progression or toxicity.
ANTICIPATED STUDY DATES	Planned Start Date: February 2011 Planned Recruitment Closure: February 2013 Planned End Date: February 2014

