3.2.4 Clinical Studies with Bavituximab

Bavituximab is currently being investigated in patients with refractory advanced solid tumor malignancies and in patients with chronic hepatitis C virus infection (HCV) by Peregrine Pharmaceuticals.

Antiviral studies

Three clinical studies to evaluate the antiviral activity of bavituximab have been conducted or are ongoing. In a phase 1 study, 30 patients with chronic HCV infection were treated with a single dose of bavituximab at 0.1, 0.3, 1, 3, or 6 mg/kg. Patients receiving 6 mg/kg had a slight elevation in d-dimer, which returned to baseline as the antibody cleared from circulation. Transient reductions in viral load suggestive of anti-viral activity were observed at all dose levels. In a phase 1b study, 24 patients with chronic HCV were treated twice weekly with bavituximab at 0.3, 1, 3, or 6 mg/kg. Bavituximab exhibited predictable PK characteristics in both studies. All dose levels tested exhibited transient anti-viral activity, and 3 mg/kg appeared most active.

Cancer studies

Five studies with bavituximab in oncology indications have been conducted or are ongoing.

A phase 1 IND study in patients with advanced solid tumor malignancies was conducted to evaluate the safety, PK, and maximum tolerated/effective dose of bavituximab given as a single agent weekly for 4 weeks. Twenty-six patients were enrolled at 0.1, 0.3, 1, or 3 mg/kg. Most adverse events (AEs) related to bavituximab were mild or moderate, and linear PK characteristics were observed. Pulmonary embolism, considered serious and related to study drug, was the only dose limiting toxicity observed in the study. This adverse event was grade 4 in nature and occurred in one patient 7 days after initiation of therapy.

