Another study in advanced solid tumor malignancies was conducted using 3 mg/kg bavituximab weekly for 8 weeks in combination with chemotherapy (docetaxel, gemcitabine, or paclitaxel + carboplatin). Two patients in the docetaxel arm discontinued bavituximab treatment after developing severe infusion reactions; urticaria in both patients. In response to these observed infusion reactions, the protocol was amended to add instructions for premedication with a steroid and an antihistamine prior to each bavituximab infusion. One patient with stage IV ovarian carcinoma developed grade 4 refractory hypotension 2 days after receiving the initial dose of docetaxel and bavituximab and expired 1 week after the initial serious adverse event (SAE); these events are considered probably study drug related. Twelve of the 14 patients enrolled were evaluable for tumor response using Response Evaluation Criteria in Solid Tumors (RECIST). Three patients achieved partial response (PR) (2 in the paclitaxel/carboplatin arm, 1 in the gemcitabine arm) and continued bavituximab maintenance on compassionate grounds, 3 patients demonstrated stable disease, and 6 patients had tumor progression. (26)

Two non-IND phase 2 studies are ongoing in locally advanced or metastatic breast cancer, to investigate the safety and efficacy of bavituximab 3 mg/kg weekly in combination with carboplatin plus paclitaxel in 28-day cycles or docetaxel in 28-day cycles. Fifteen of 46 patients treated in PPHM 0702 experienced AEs considered related to bavituximab, including fatigue and anemia, and 4 patients experienced drug-related severe adverse events (SAE);

among stage A patients (in a Simon 2-stage design) in the intent-to-treat (ITT) group, the ORR was 60% (9/15). Thirty-six of 46 patients treated in PPHM 0704 experienced AEs considered related to bavituximab, including epistaxis, infusion-related reaction, nasal dryness, and nail bed bleeding, and 4 patients experienced drug-related SAEs; the ORR for all enrolled patients was 61% (28/46). In PPHM 0702 and 0704 there were 6 grade 3 or 4 AEs (6 of 92 patients, incidence of 6.5%). The median number of bavituximab doses for a grade 3 or 4 adverse event was 15 (range, 8 to 20). (27, 28)

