4.2.2 Phase II Component

Patients will be eligible for enrollment on study if Histologically confirmed hepatocellular carcinoma.

Patients also need to have advanced disease as defined previously in section 4.1. Attending surgical oncology, hepatologists and liver transplant physicians (surgeons or hepatologists) with expertise in the management of HCC will assess suitability of surgical resection and liver transplantation at participating sites.

All patients will initially be staged with a liver protocol CT or MRI of the abdomen. A chest CT will be done if there is a concern for intra-pulmonary metastases.

Prior to the initiation of therapy serological markers (alpha-fetoprotein and viral hepatitis markers, including hepatitis C antibody and hepatitis B surface antigen), serum, image guided core biopsy of an intra-hepatic tumor (performed for clinical care. If the biopsy is performed for clinical care, additional needle core specimens (up to 3) will be obtained in addition to the number needed for

histopathological analysis. This is of minimal additional risk as same needle tract will be used to acquire additional specimens.

Bavituximab will be administered on a weekly schedule until intolerable toxicity, or the development of any of the criteria for requiring removal from the study as outlined in Section 14 of the protocol. Sorafenib will be administered on a daily schedule until intolerable toxicity, or the development of any of the criteria for requiring removal from the study as outlined in Section 14 of the protocol. The dose of bavituximab for the phase II component will be the maximum tolerated dose determined in the phase I component. In the phase I component, bavituximab will be started at 0.3 mg/kg and will be escalated pending DLT to 1.0 mg/kg and 3.0 mg/kg. These doses will be given intravenously over 90 minutes starting on day Sorafenib will be initially dosed at 200 mg orally twice a day and escalated to the target dose of 400 mg orally twice a day at the discretion of the treating medical oncologist. Sorafenib will be started within 3 days of the initial bavituximab dose.

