11.0 DOSE-LIMITING TOXICITIES-PHASE I COMPONENT

The phase I component of the study will consist of a traditional 3+3 dose escalation rule with the dose of sorafenib remaining constant and the dose of bavituximab escalating up to 3.0 mg/kg weekly to determine the maximum tolerated dose (MTD) that will be used during the phase II component. Sorafenib has been demonstrated in multiple phase I and II studies in advanced HCC to have minimal toxicity and to be safe, therefore doses will be constant. (13,14) Cohorts of three patients will be assigned to one dose level of bavituximab starting at 0.3 mg/kg weekly. Only the first cycle of therapy (4 doses of bavituximab and 4 weeks of sorafenib constitutes a cycle) will be used to determine dose limiting toxicity (DLT). The patients will be followed for thirty days following the end of the first cycle for adverse events. These adverse events will be submitted to the Data Safety Monitoring Committee for evaluation. During this thirty-day period and beyond patients will be administered sorafenib at the discretion of the treating oncologist. Patients will be enrolled into the next highest drug cohort only after 3 or 6 patients have completed the first cycle of therapy. The number of observed toxicities is counted and the traditional escalation rule applied:

- No toxicity: the next three patients will be assigned to next higher dose level (3.0 mg/kg of bavituximab is the highest dose assigned).
- At least two toxicities: the MTD is exceeded and the phase I component of the trial will be stopped with the next lowest dose to be defined as the MTD that will be used in the phase II component.
- One toxicity: the cohort will be expanded to 6 patients.
 - One DLT within the last six patients: The next cohort of three patients will be assigned to the next highest dose level
 - At least two DLTs within the last six patients: the MTD is exceeded and the phase I component of the trial will be stopped with the next lowest dose to be defined as the dose that will be used in the phase II component.

The Data and Safety Monitoring Committee and investigators as described below will regularly review all adverse events. The study will utilize the Common Terminology Criteria for Adverse Events (CTCAE) version 4.0 for grading of all adverse events related to treatment.

The following will be considered a dose-limiting toxicity:

- Grade 4 neutropenia and thrombocytopenia ≥ 7 days (absolute granulocyte count $< 0.5 \times 10^9/L$)

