15.1 Sample size calculation

The phase I component of the study will consist of a traditional 3+3 dose escalation rule with 3 or 6 patients in each cohort, the process for dose escalation is outlined in section 4.1.

The median TTP of patients with advanced HCC treated with sorafenib therapy is 5.5 months. Using this as a benchmark, we will enroll 38 patients, which will allow us to differentiate between a median TTP of 5.5 months and 8.3 months with 80% power and a two-sided significance level of 10% assuming a 24-month accrual and a 12-month follow-up period. TTP will be calculated from initiation of therapy to disease progression (intention to treat) as outlined in section 13.0. Removal from study as outlined in section 14 will be a censored event.

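### Section 11 can carry a dose cleared on 0 of 3 patients into Phase II; confirming it at six is a cheap improvement that fits within the 18 Phase I patients already planned

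*Combined protocol and SAP*

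**What the plan says.** Section 15.1 describes a "traditional 3+3 dose escalation rule with 3 or 6 patients in each cohort", and the synopsis expects "Phase I component- 9-18 patients". Section 11 gives the rule for three bavituximab levels (0.3, 1.0 and 3.0 mg/kg weekly), counting DLTs in the first four-week cycle only.

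- 0 of 3: "No toxicity: the next three patients will be assigned to next higher dose level".
- Exactly one in 3: the level is expanded to six. It passes if the count stays at one of six.
- At least two, in three or in six: the level is exceeded and Phase I stops. In the three-patient case the wording is "with the next lowest dose to be defined as the MTD that will be used in the phase II component", and the six-patient case reads almost the same.

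Section 4.2.2 then says: "The dose of bavituximab for the phase II component will be the maximum tolerated dose determined in the phase I component". Phase II plans 38 patients.

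The available text has no step that adds patients at the level below a failed one. It has none at 3.0 mg/kg after 0 of 3, and it does not say what happens if 0.3 mg/kg itself is exceeded, since no lower dose exists. Section 15.1 refers to Section 4.1 for the escalation process, and the figures in Sections 4.1 and 4.2.1 could not be seen.

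**The concern.** The selected dose goes to 38 patients with no fixed number of cycles. Within this trial, its tolerability alongside sorafenib may rest on three patients observed for one DLT cycle. Some of those patients may not have reached full-dose sorafenib, because Section 4.2.1 starts it at 200 mg twice daily and leaves escalation to the treating oncologist.

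Three clean patients exclude little: a level with a true 40% DLT rate gives 0 of 3 with probability 0.6³ = 0.216. If the dose is set too high, Section 9.4 lists no bavituximab-specific delay or modification apart from the removal criteria in Section 14. Phase II has committee review and stopping for individual patients, but no stated toxicity threshold for rejecting the dose.

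**Working it through.** **The plan's own range.** 3 levels × 3 patients = 9 and 3 levels × 6 patients = 18, so 9-18 reproduces when all three levels are opened.

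**DLT rates.** The documents give no cycle-1 DLT rate for the combination, so all rates are assumed.

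- Flat 1/26 = 3.8%: Section 3.2.4, one DLT with bavituximab alone; "Twenty-six patients were enrolled at 0.1, 0.3, 1, or 3 mg/kg".
- Flat 6/92 = 6.5%: Section 3.2.4, grade 3-4 events in the two breast cancer studies.
- Flat 20%: the sorafenib grade 3 rates in Section 3.1 added together, 8 + 8 + 2 + 2.
- Flat 28.5%: Section 3.2.4, grade 3-4 events in the lung cancer study.
- Rising patterns 5/10/20%, 5/10/40% and 5/40/50%: no source, for illustration only.

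The 20% and 28.5% figures are not cycle-1 DLT rates and serve only as high markers.

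**One level, true rate p.**

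- Present rule: P(accept) = (1−p)³ + 3p(1−p)⁵.
- Confirmed at six: P(accept) = (1−p)⁶ + 6p(1−p)⁵.
- At p = 0.4: 0.216 + 0.093 = 0.309 now, against 0.047 + 0.187 = 0.233.

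**How many patients a step-down dose rests on.** Given that a level passed, it was cleared on three with probability 1/[1 + 3p(1−p)²]. This gives 0.904, 0.854, 0.72 and 0.696 at the four flat rates. At 5/10/20% and 5/10/40%, where either lower level can be named, exact enumeration gives 0.825 and 0.814. The range is therefore about 70-90%.

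**Whole rule at 5/40/50%.**

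- P(0.3 mg/kg passes) = 0.95³ + 3(0.05)(0.95)⁵ = 0.973.
- Now: P(1.0 or 3.0 mg/kg is named) = 0.9734 × 0.3093 = 0.301. Confirming only 3.0 mg/kg leaves this unchanged, because a trial failing there falls back to 1.0 mg/kg.
- Confirmed: P(at most 1 of 6 at 50%) = 0.1094, so 0.9734 × [0.3093 × 0.1094 + (1 − 0.1094) × 0.2333] = 0.235.

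**Low toxicity, flat 1/26.** A level passes with probability 0.9838 now and 0.9800 at six. 3.0 mg/kg is named with probability 0.9838³ = 0.952 now (if 0 of 3 there ends Phase I) and 0.9838² × 0.9800 = 0.949 with confirmation.

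**Ceiling.** No level ever exceeds six patients, so the maximum is 3 × 6 = 18 on every path. With confirmation, a trial that names a dose uses 9 to 18 Phase I patients, or 47 to 56 with the 38 in Phase II.

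**Price of confirming**, present rule with 0 of 3 at 3.0 mg/kg ending Phase I, against the change:

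| Assumed rates | Mean Phase I size | Other effect |
|---|---|---|
| Flat 1/26 | 9.8 → 12.5 | 3.0 mg/kg named 95.2% → 94.9% |
| Flat 20% | 9.2 → 10.8 | No dose named 29.1% → 30.8% |
| Flat 28.5% | 7.8 → 9.0 | No dose named 47.5% → 51.2% |
| 5/10/20% | 10.7 → 13.1 | 3.0 mg/kg named 63% → 58% |
| 5/40/50% | 8.8 → 11.5 | Level ≥ 40% named 30.1% → 23.5% |

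**The case against.** The strongest reply is that this is the traditional 3+3, prespecified as such, and that nothing in the plan promises six patients at the MTD. That stands. A reader might infer a contradiction or a miscalculation, and the documents support neither.

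Second, a reader might take the frequency of step-down as a measure of harm. It is not. At 5/10/40% the step-down names the dose in 70% of trials, but most of these land on 1.0 mg/kg, whose assumed rate is 10%, so the rule has chosen well. The frequency also depends on the unseen top-dose step: if 3.0 mg/kg is already confirmed at six, it becomes 77%, and 35% becomes 40% at 5/10/20%. With the top step held at six, confirming the lower levels moves selection of 1.0 mg/kg at 5/10/40% only from 67.6% to 66.1%, a small loss.

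Third, there is outside evidence on the dose. Section 3.2.4 reports: "Another study in advanced solid tumor malignancies was conducted using 3 mg/kg bavituximab weekly for 8 weeks in combination with chemotherapy". Together with the breast and lung cancer studies that makes 14 + 46 + 46 + 49 = 155 patients at 3 mg/kg weekly. This supports the bavituximab dose, but the partner drugs were cytotoxic chemotherapy and not sorafenib. Section 11 also follows patients for thirty days after cycle 1, adjacent levels add some combination data, and the monitoring committee reviews serious events as they are reported. These safeguards are real, although none sets a rule for rejecting the dose.

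Fourth, one could infer that the text definitely ends Phase I after 0 of 3 at 3.0 mg/kg. Section 11 is silent there and the figures may show six patients. A figure might also show a step on the way down, although Section 11's wording on stopping is explicit.

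Fifth, the expected range of 9-18 could be called wrong because the rule can stop at 3 or 6. The row gives an expected number, holds if all levels are opened, and enters no analysis. No change is needed there.

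Finally, a DLT check on the first Phase II patients would need no added patients. It is a reasonable alternative, but the plan does not contain it.

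**Conclusion.** The point holds as an optional, inexpensive improvement. Two facts need no assumed rate: the written rule lets a level cleared on 0 of 3 become the Phase II dose, and confirming at six cannot take Phase I above 18.

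The benefit depends on the unknown DLT rates. It is about 8 percentage points for a single level with a true 40% rate (31% against 23%), and 6.6 points (30.1% against 23.5%) at 5/40/50%, a pattern without a source in the documents. If bavituximab adds as little toxicity as 1/26 suggests, confirmation changes almost nothing. When a step-down does name the dose, that dose rests on three patients in about 70-90% of cases at the rates examined. Confidence is medium, because the figures could not be seen and no combination DLT rate is available.

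**What to change.** Add to Section 11:

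*Before Phase II opens, the selected level is expanded to six patients if it does not already have six. It is the Phase II dose if at most 1 of 6 has a cycle-1 DLT; otherwise the next lower level is expanded and judged in the same way. If 0.3 mg/kg is exceeded, no MTD is declared and Phase II does not open.*

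If a figure already requires six at 3.0 mg/kg, the expansion is new only for the step-down. The last sentence is needed in either case.

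Cost: on average 1.2 (flat 28.5%) to 2.7 (flat 1/26) more Phase I patients, within the planned 18. Each level confirmed takes one cycle, 28/30.44 = 0.9 month, plus accrual of three patients. Section 15.1 sizes the study "assuming a 24-month accrual and a 12-month follow-up period". With even accrual of 56 down to 38 patients over those 24 months, three patients take 3/(56/24) = 1.3 to 3/(38/24) = 1.9 months. That makes 2.2 to 2.8 months per level, and the same again for each further step down. A tolerable dose is also rejected slightly more often: at 5/10/20%, 3.0 mg/kg is selected in 58% rather than 63% of trials, if 0 of 3 there now ends Phase I.

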9.3 Supportive Care Guidelines for Therapy (Bavituximab and Sorafenib)

- Recommended anti-emetics for therapy regimen
 - Bavituximab and sorafenib are minimal risk emetogenic regimens. The anti-emetic regimen is per institution guidelines and typically includes no additional anti-emetic therapy.
- Recommended pre-medication regimen to reduce infusion reactions
 - The recommended pre-medication regimen includes the following prior to bavituximab infusion prior to infusion:
 - Hydrocortisone 250 mg IV on all days of IV therapy
 - Diphenhydramine 50 mg IV on all days of IV therapy

The dose of hydrocortisone may be reduced or omitted where medically indicated (i.e. diabetes).

Concurrent supportive care is not restricted, including the use of narcotics for pain control, anti-emetics or anti-diarrheals. No concurrent chemotherapy, immunotherapy, radiation therapy or chemoembolization is permitted during therapy. Use of epoetin alfa and white blood cell support is permitted at the discretion of the treating physician.

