- platelet count $< 25,000$
- ALT or AST levels \geq grade 3 adverse event for 7 days
- \geq grade 3 adverse event for any non-hematologic toxicity (excluding alopecia and non-premedicated nausea/vomiting) attributable to drug therapy by the definition of definite or probable and not possibly. In the SHARP trial patients in the placebo arm had over a 50% \geq grade 3 adverse event rate due to the comorbidities seen in the patient population with advanced HCC.

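### The Phase I DLT definition excludes non-premedicated nausea/vomiting without defining the term or capping grade or duration, so a first drug-attributed grade 4 event would typically not count

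*Combined protocol and SAP*

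**What the plan says.** Section 11.0 lists the dose-limiting toxicities for the 3+3 escalation. The non-hematologic item covers events of grade 3 or higher, "excluding alopecia and non-premedicated nausea/vomiting", provided they are "attributable to drug therapy by the definition of definite or probable and not possibly". The exclusion carries no upper grade, no time limit and no condition on response to treatment, and *non-premedicated* is not defined anywhere.

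Section 9.3 says "Bavituximab and sorafenib are minimal risk emetogenic regimens" and continues: "The anti-emetic regimen is per institution guidelines and typically includes no additional anti-emetic therapy". It also says: "Concurrent supportive care is not restricted, including the use of narcotics for pain control, anti-emetics or anti-diarrheals". Hydrocortisone and diphenhydramine appear there under a separate bullet, as protection against infusion reactions; Section 5.1 gives the same purpose and makes them mandatory before each infusion.

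The window for counting is short: "Only the first cycle of therapy (4 doses of bavituximab and 4 weeks of sorafenib constitutes a cycle". Within it, the rule turns on one or two patients. For an expanded cohort it reads "At least two DLTs within the last six patients: the MTD is exceeded". The dose that results is carried into Phase II.

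**The concern.** An exclusion tied to absence of premedication makes sense where anti-emetic prophylaxis is routine, because it sets aside events that ordinary care would have prevented. Here prophylaxis is typically not given, so the exclusion becomes the usual case. A patient managed in the normal way who has a first severe episode would be classed as non-premedicated, and nothing in Section 11.0 brings the event back into the count if it reaches grade 4.

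The neighbouring criteria are built differently. Neutropenia and thrombocytopenia are qualified by grade and by lasting at least 7 days, and transaminase elevations by grade and by 7 days' duration. Nausea/vomiting is qualified only by what was given beforehand.

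At stake is the MTD, which is the Phase I primary objective. One uncounted event can change 1/3 to 0/3 (clear the level instead of expanding the cohort), 2/3 to 1/3 (expand instead of stopping) or 2/6 to 1/6 (clear instead of stopping).

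**Working it through.** **Step 1: the two readings of *premedicated*.**
- *Anti-emetic prophylaxis.* This fits the subject of the exclusion, and Section 9.3 lists anti-emetics and infusion-reaction premedication separately. Since anti-emetics are typically not added, most first events fall under the exclusion. Events arising after prophylaxis has begun do count.
- *Hydrocortisone and diphenhydramine.* These are given before every infusion, although Section 9.3 allows hydrocortisone to be reduced or omitted where medically indicated. Nearly every patient is then premedicated, nearly every event counts, and the exclusion does almost nothing.

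The first reading is the more natural, but two investigators could classify the same event in opposite ways.

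**Step 2: the plan's own figure.** Three dose levels with 3 or 6 patients each give 3 × 3 = 9 to 3 × 6 = 18, which matches the 9 to 18 Phase I patients in Section 1.0. No stated number is in dispute.

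**Step 3: size of the effect.** Under the Section 11.0 rule a level is cleared on 0/3, or on 1/3 followed by 0/3. With per-patient DLT probability q, the stop probability is

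S(q) = 1 − [(1−q)³ + 3q(1−q)⁵], where q = 1 − (1−b)(1−r·v).

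Here b is the rate of other DLTs, v is the cycle 1 rate of drug-attributed nausea/vomiting of grade 3 or higher, and r is the share of those events that count. The documents give none of these, so all are assumed. The formula treats the two kinds of DLT as independent.

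Worked example, b = 0.10:
- Events excluded (r = 0): q = 0.10, so S = 1 − [0.7290 + 0.1771] = 0.0939.
- All counted (r = 1), v = 0.02: q = 1 − 0.90 × 0.98 = 0.118, so S = 1 − [0.6861 + 0.1890] = 0.1249.

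| b | v | S, none counted | S, all counted | Shift (points) | Shift if half count (points) |
|---|---|---|---|---|---|
| 10% | 1% | 9.39% | 10.90% | 1.52 | 0.75 |
| 10% | 2% | 9.39% | 12.49% | 3.11 | 1.52 |
| 20% | 1% | 29.14% | 30.88% | 1.74 | 0.87 |
| 20% | 2% | 29.14% | 32.62% | 3.48 | 1.74 |

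Shifts are taken before rounding. The column with all events counted is an upper bound on the change: some events already count today (those after prophylaxis), and a sensible fix would leave some excluded. As a stress case, v = 5% with all counted gives S of about 17.6% (b = 10%) and 37.8% (b = 20%), but that rate sits poorly with a regimen described as minimally emetogenic.

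**Step 4: would such an event be seen at all?** The probability of at least one in n patients is 1 − (1−v)ⁿ. For n = 9 and 18 this is 8.7% and 16.6% at v = 1%, and 16.6% and 30.5% at v = 2%.

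**Step 5: what the documents suggest about the rate.** Section 12.2 calls nausea and vomiting with bavituximab infrequent and self-limiting. Section 3.2.4 reports for the two breast cancer studies: "The median number of bavituximab doses for a grade 3 or 4 adverse event was 15 (range, 8 to 20" doses. Those events came after more doses than the four in the DLT window here. Both statements point to the low end, although neither concerns the combination with sorafenib.

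**The case against.** The strongest reply is that the concern rests on one reading of an undefined word. For study treatment the protocol uses pre-medication only for the steroid and antihistamine, never for anti-emetics, and on that reading nearly all events count. This stands as a reason to call the text ambiguous. It does not rescue the text, because the exclusion would then have almost no content.

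A reader might infer that severe nausea/vomiting can never be a DLT in this trial. The documents do not support that. Section 9.3 speaks of typical practice under institution guidelines, anti-emetics are unrestricted, and with four weekly doses in the window an event arising after prophylaxis has begun would count. Any other drug-attributed non-hematologic event of grade 3 or higher, including a severe consequence of vomiting recorded in its own right, also counts.

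A reader might also infer that a grade 3 event persisting despite anti-emetics is plainly excluded. That is less clear than for a grade 4 event. Sorafenib is taken twice daily, so doses after anti-emetics start are taken under anti-emetic cover, and an event that continues through them is no longer obviously non-premedicated. Section 11.0 does not settle it.

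Finally, oversight remains. The monitoring committee reviews all adverse events, its chair can act at once on serious ones, and unacceptable toxicity ends treatment. This protects the patient, but no stated rule adds the event to the 3+3 count.

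**Conclusion.** The point holds as a minor defect of wording in a rule that decides the MTD. On the more natural reading, a first grade 4 nausea/vomiting event judged definitely or probably drug-related would typically not count; for an unresolved grade 3 event the text is arguable. On the other reading the exclusion is nearly empty.

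The practical effect is probably small: at most about 1.5 to 3.5 points in the stop probability per dose level, given assumed event rates of 1% to 2% and other DLTs at 10% to 20%. It would be stronger to say that the MTD is likely to be set too high. The documents give no rate from which that could follow, and what they do say points to rare events.

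**What to change.** In Section 11.0, keep the exclusion but narrow it: *excluding alopecia and grade 3 nausea/vomiting that arises without anti-emetic prophylaxis and resolves to grade 2 or lower within 72 hours of starting anti-emetic treatment*. The 72 hours is a proposed value for the sponsor to confirm. Dose-limiting events would then include all grade 4 nausea/vomiting, grade 3 events that persist beyond that time, and events of grade 3 or higher that arise despite anti-emetic prophylaxis.

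The condition about prophylaxis should stay. Excluding every grade 3 event that resolves with anti-emetics would drop breakthrough events under prophylaxis, which count today, and the net direction of the change would then be unclear.

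The cost is one line of text, with no added patients, visits or procedures. Escalation becomes slightly more conservative, by no more than the upper bound above at the assumed rates, and by 0.75 to 1.74 points if half of the events qualify.
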